9.3 Randomization and Stratification

We will conduct an open-label, randomized, controlled, two-arm, clinical strategy trial for PrEP adherence. Subjects will be randomized (1:1) to one of two arms: the **Standard of Care** (SoC) or the **iTAB** enhanced adherence arm. Randomization will be stratified by clinic site. A total of 400 subjects (200 per arm) will be randomized and followed in the study for 48 weeks after enrollment of the last subject.

Once eligibility and consent are confirmed, randomization will occur using the web-based CFAR BIT data management system.

9.4 Study Power and Sample Size Justification

The primary objective for this study is to compare the proportion of subjects that reach the composite endpoint, defined as: continued retention and adherence to PrEP. Sample size calculations were based on a two-sided, two- sample binomial test to compare the differences in composite endpoint proportions between the intervention arm and the standard of care arm. Since attrition is a component of the composite endpoint, attrition rates are not used as an adjustment in the power calculations. Assuming 200 subjects per group in each of the two groups (for a total of 400 subjects) and alpha set to 0.05, we have 94% power to detect a difference of 15%, assuming that 30% with a composite endpoint rate in standard of care and that 15% with endpoint in the intervention arm. We have 84% power to detect as small a difference of 13% between the two groups (i.e., 30% versus 17%).

9.5 Monitoring

The study team will review all adverse events during PrEP therapy by cumulative reports, both arms combined in aggregate, on a monthly basis. Adverse events will be graded using the ACTG toxicity grading scale and recorded using standard CCTG AE electronic data capture. The study investigators will monitor safety events in aggregate on monthly team calls. An independent Data Safety and Monitoring Board (DSMB) will not be used for this study.

9.6 Analyses

9.6.1 Statistical Analysis Plan

In general, analyses will incorporate the modified intent-to-treat (mITT) principle, namely, all randomized participants dispensed study medication will be included in the analysis. The primary analysis compares the iTAB enhanced proportion of adherence to the SOC arm.

For all secondary analyses of interest, no adjustments for multiple comparisons will be made and a p-value of 0.05 will be considered statistically significant. Demographic and baseline measurement variables will be summarized via standard descriptive statistics. There will be no interim analyses for futility or efficacy conducted.

9.6.2 Analysis of Primary Outcome

The primary analysis will use a two-sample binomial test for proportions to determine if the intervention arm will produce an improved composite endpoint rate compared to the standard of care arm. Fisher's exact test will be used along with a 95% confidence interval. As a sensitivity analysis, the two components of the composite primary endpoint will be analyzed separately (retained on PrEP and Adherence > 90%). A Fisher's exact test will be used to compare rates of study discontinuation between the active intervention arm versus standard of care arm.

9.6.3 Analysis of FTC Plasma Concentrations

With repeated qualitative FTC assays in each subject over time, adherence will be defined using a continuous and categorical metric. The percent adherence, calculated as number of detectable samples divided by total number of samples measured, will be compared between intervention and control using a two-sample t-test (or an appropriate non-parametric alternative if parametric assumptions fail). For strict mITT analyses, subjects that are missing a FTC concentration at any time point (whether due to missed visit or TDF/ FTC discontinuation) will be defined as having an undetectable FTC concentration while per protocol analyses will consider only available data (i.e., no imputation for missing values). A categorical metric of good adherence (> 90% of concentrations detectable) will be compared between intervention and control with the Fisher's exact test.

9.6.4 Analysis of additional Secondary outcomes

The incidence rate of STI will be compared between SOC and ALERT- iTAB intervention arms using Fisher's exact test as will the rate of HIV seroconversion between groups (the rate of new HIV is expected to be low). In order to evaluate hypothesis 3c (factors associated with the composite primary endpoint of on therapy and adherence > 90%), multivariable logistic regression models will also be used. A subgroup analysis by treatment arm will be conducted, looking at each arm separately. Descriptive analysis will be performed within each subgroup

to compare adherent versus non-adherent subjects. The models will include the following potential covariates: demographics, ongoing substance use, untreated mental illness, socioeconomic status, HIV risk transmission behaviors, low health/ HIV and system literacy, fear of disclosure and non-English. Further, any covariates (including stratification factors) that are simultaneously unbalanced at baseline (univariate $p < 0.10$) and associated with the outcome (univariate $p < 0.15$) will be included in the model as observed confounders. Sub-group analyses based on race/ ethnicity, gender, primary language, socioeconomic status by randomization arm will also be conducted. Secondary endpoints for adherence will be analyzed analogously to the primary endpoint.

- 9.6.5 Safety and tolerability of daily TDF/FTC given for PrEP including discontinuation for any adverse event, serious adverse events and adverse events (grade 2 or higher) will be compared between study arms. Descriptive statistics will be used to characterize safety events. Fisher's exact test will be used to compare discontinuation rates due to safety and incidence rates of adverse events and serious adverse events. The time to TDF/ FTC discontinuation for adverse events will be compared between groups using the log-rank test and plotted using Kaplan-Meier curves. Similar analysis will be done for the time to discontinuation for any reason (including drop-out or subject electing to stop PrEP due to lack of perceived risk for HIV).

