- 1.2.5 To determine the rate of HIV seroconversion in PrEP users and compare the iTAB to SOC arms for number of new infections as a proportion at 48 weeks and end of study.
- 1.2.6 To measure acquisition of other sexually transmitted infections (STIs); the proportion of subjects with any new STI at any site will be compared between the iTAB to SOC arms at 48 weeks and through the end of the study.
- 1.2.7 To evaluate changes in risk behavior after initiation of PrEP (risk compensation) comparing baseline to subsequent visits for number of HIV positive/unknown status partners and any unprotected anal intercourse with an HIV positive/ unknown status partner.
- 1.2.8 To evaluate the safety and tolerability of daily TDF/FTC given for PrEP including discontinuation for any adverse event, serious adverse events and adverse events (grade 2 or higher).

1.3 Exploratory Objectives:

- 1.3.1 To describe changes over time of self-reported adherence in real time by texting.

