5.1.3 Duration

Subjects will participate in this study until 48 weeks beyond the enrollment of the last subject with a maximum duration of 96 weeks for any subject. Subjects may receive study treatment until their last study visit.

Subjects will receive study treatment for the duration of the study unless they meet criteria for discontinuation.

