Descriptive analysis will look at self-reported adherence, FTC adherence and TFV-DP adherence measures by visit. Continuous outcome will be summarized with N, min, Q1, median, Q3, and max, by study arm and overall. Binary endpoint will be summarized with frequency tables, by study arm and overall. Wilcoxon rank sum test will be used for comparison for continuous outcome; Fisher's exact test will be used for binary outcome.

Statistical Inference

A logistic regression model will be performed to compare the adherence over 48 weeks between the two groups. The model will include baseline factors (refer to the baseline variable list) as covariates if they are found unbalanced between the study arms (with $p < 0.1$) and also univariately associated with the outcome ($p < 0.15$). Interactions between each of the covariates and study arm will also be assessed individually. Significant interactions ($p < 0.05$) will be included in the final model.

7 Evaluation of Secondary Objectives

7.1 Secondary Objective 1

To determine factors associated with poor adherence/lost to PrEP in study participants. Factors will include demographics, ongoing substance use, untreated mental illness, socioeconomic status, low health/HIV and system literacy, fear of disclosure and non-English language.

This objective will be assessed along with the primary objective analysis. The final primary multivariable model will be able to answer this question.

7.2 Secondary Objective 2

To determine the rate of HIV seroconversion in PrEP users and compare the iTAB to SoC arms for number of new infections as a proportion at 48 weeks and end of the study.

Number and proportion of subjects with HIV-seroconversion at 48 weeks will be summarized by study arm and overall. Fisher's exact test will be used for comparison. Same analysis will also look at the rate of seroconversion during the whole study period.

7.3 Secondary Objective 3

To measure acquisition of other sexually transmitted infections (STIs); the proportion of subjects with any new STI at any site will be compared between the iTAB to SoC arms at 48 weeks and end of the study.

Any new STI will be defined as positive results from Gonorrhea (GC) or Chlamydia (CT) at any site or positive syphilis RPR result with titer $>1:4$ based on the STI form collected after baseline visit.

Sensitivity analysis will also be performed looking at STI by testing as well as self-reported STI (outside diagnosis) based on the clinical assessment form.

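### End-of-study STI is compared by Fisher's test on crude proportions with no allowance for time at risk, which biases against iTAB if iTAB improves study retention

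*Protocol*

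**What the plan says.** **Test and label.** Protocol 9.6.4 says of the first outcome: "The incidence rate of STI will be compared between SOC and ALERT- iTAB intervention arms". The test it names is Fisher's exact. HIV is put under the same test in the next clause: "as will the rate of HIV seroconversion between groups (the rate of new HIV is expected to be low". The words incidence rate are used for STI only; HIV is called a rate.

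**Objectives.** Protocol 1.2.5 sets the HIV measure as "number of new infections as a proportion at 48 weeks and end of study". Protocol 1.2.6 sets the STI measure as a proportion too: "the proportion of subjects with any new STI at any site will be compared between the iTAB to SOC arms at 48 weeks", and again through end of study.

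**SAP.** Section 7.2: "Number and proportion of subjects with HIV-seroconversion at 48 weeks will be summarized by study arm and overall", with Fisher's test, and then "Same analysis will also look at the rate of seroconversion during the whole study period". Section 7.3 defines a new STI as any qualifying positive after baseline but names no test, so Protocol 9.6.4 supplies the only one. The SAP overrides Protocol section 9 where they differ (Protocol 9.0), but here it is silent.

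**Follow-up and testing.** Protocol 5.1.3 has participants stay "until 48 weeks beyond the enrollment of the last subject with a maximum duration of 96 weeks for any subject". SAP section 2 gives a limit of about 2.5 years. STI tests are at week 0 and every 24 weeks (Protocol 6.2.3), so a completer has two post-baseline tests by week 48 and four by week 96. Rapid HIV tests are at every visit. Missed visits end participation (Protocol 8.1.7 and 8.1.8). People who stop drug may stay on schedule with STI and HIV testing (Protocol 6.4.1).

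**Not stated for STI or HIV.** Neither document gives a denominator, person-time, a censoring rule or a time-to-event analysis. Kaplan-Meier and log-rank methods are planned only for discontinuation.

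**The concern.** An ever-positive proportion rises with time observed and with number of tests. The trial tests whether iTAB improves retention as well as adherence. Only the iTAB arm has coordinator calls after unanswered messages and a contact plan for missed appointments (Protocol 3.2). If this lengthens study follow-up, the iTAB arm has more opportunity for an infection to occur and be found, even when the infection rate is identical.

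The bias therefore appears when the intervention succeeds, and it runs against the intervention. Risk compensation is itself an objective (Protocol 1.2.7), so a spurious STI excess in the iTAB arm could be read as riskier behavior. The wording adds to the difficulty: a result labelled an incidence rate would in fact be a crude proportion.

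**Working it through.** **Check of the test routine.** Protocol 9.4 states 94% power for 30% vs 15% and 84% for 30% vs 17%, with 200 per arm and two-sided alpha 0.05. Exact enumeration of Fisher's test gives 94.0% and 84.5%, so both reproduce. The documents give no figure for STI or HIV.

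**Inputs.** From the documents: 200 per arm, follow-up 48 to 96 weeks, STI tests every 24 weeks. Assumed: a constant STI rate λ of 0.2, 0.5 or 0.9 per person-year, equal in both arms; HIV rate 0.02; exponential study dropout; planned follow-up uniform over 48 to 96 weeks; all randomized as denominator. Week-48 dropout of 30% vs 15% is an upper bound borrowed from Protocol 9.4, as if the whole powered difference in the composite were study dropout. Milder gaps are shown beside it.

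**Formulas.** Let a = 48/52 = 0.923 years, q = week-48 dropout, d = −ln(1−q)/a, s = λ + d.
- Week 48: p = (λ/s)(1 − e^(−sa))
- End of study: p = (λ/s)[1 − (e^(−sa) − e^(−2sa))/(sa)]

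**Worked case, λ = 0.5, end of study.**
- SoC, q = 0.30: d = 0.386, s = 0.886, sa = 0.818; p = 0.564 × [1 − (0.441 − 0.195)/0.818] = 0.394.
- iTAB, q = 0.15: d = 0.176, s = 0.676, sa = 0.624; p = 0.740 × [1 − (0.536 − 0.287)/0.624] = 0.445.
- Risk ratio 0.445/0.394 = 1.13. Fisher's test rejects 14.9% of the time, almost always against iTAB.

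**All STI cases, no true difference** (SoC % vs iTAB %; risk ratio; Fisher rejection):

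| Dropout SoC / iTAB | λ | Week 48 | End of study |
|---|---|---|---|
| 30% / 15% | 0.2 | 14.3 vs 15.6; 1.09; 4.9% | 18.8 vs 21.4; 1.14; 8.0% |
| 30% / 15% | 0.5 | 31.5 vs 34.3; 1.09; 7.5% | 39.4 vs 44.5; 1.13; 14.9% |
| 30% / 15% | 0.9 | 48.6 vs 52.7; 1.08; 10.9% | 57.5 vs 64.0; 1.11; 23.1% |
| 25% / 15% | 0.2 to 0.9 | 1.05 to 1.06; 4.1 to 6.9% | 1.07 to 1.09; 5.5 to 12.2% |
| 20% / 15% | 0.2 to 0.9 | 1.03; 3.7 to 4.7% | 1.03 to 1.04; 4.1 to 6.0% |
| 20% / 20% | 0.2 to 0.9 | 1.00; 3.6 to 4.0% | 1.00; 3.7 to 3.9% |

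The last row shows that 48 to 96 weeks of staggered follow-up causes no bias by itself.

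**HIV at 0.02 per person-year, 30% vs 15%, end of study.** 2.1% vs 2.4%, or about 4.2 vs 4.8 infections among 200 each; risk ratio 1.15; rejection 2.2%, against 1.9% with equal dropout of 20%.

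**Detection only at the 24-weekly STI tests (simulation, 30% vs 15%).** At end of study the proportions are 32.6% vs 38.0% (λ = 0.5; rejection 17%) and 48.4% vs 56.1% (λ = 0.9; 31%). Over all three rates and both horizons, the risk ratio is 1.14 to 1.19 and rejection 6 to 31%. Interim tests for symptoms, which the protocol allows, would move results towards the table above.

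**Same simulated data by person-time.** Observed rates are equal (0.19 vs 0.19, 0.45 vs 0.45, 0.74 vs 0.74 per person-year), the rate ratio is about 1.00, and rejection is 1 to 4%.

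**The case against.** The governing text openly defines both outcomes as proportions, for which Fisher's test is a legitimate choice, and the incidence-rate label stands only in Protocol 9.6.4. These are secondary outcomes without multiplicity control. Retention is reported by arm with Kaplan-Meier and log-rank (SAP 4.2), and risk compensation is analysed within person (SAP 7.4). This stands, and it keeps the point modest. It does not supply a comparison that is fair when follow-up differs by arm.

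A reader might infer more than the documents support:
- *Unequal follow-up of 48 to 96 weeks is itself a bias.* It is not; 1:1 randomization stratified by site balances entry dates. Only differential study dropout acts.
- *Better PrEP retention means longer follow-up.* Not necessarily. Under Protocol 6.4.1, people who stop drug can stay in follow-up with testing, so the bias shrinks to the extent that they do.
- *Dropouts are scored event-free by rule.* No denominator is stated; the missing-as-failure rules concern adherence. If only participants tested after baseline are counted, the risk ratio at 30% vs 15% falls to 1.04 to 1.08 and false positives to 4 to 8%.
- *False positives near 27% are to be expected.* That figure (46.5% vs 39.3% at 0.5 per person-year) needs mean follow-up of 1.25 vs 1.0 years, or roughly 12% vs 36% dropout by week 48. That gap exceeds the 15 points powered for the whole composite.
- *Week 48 and HIV share the defect equally.* Week 48 is a fixed horizon with less inflation, and HIV is expected to be too rare for the test to be affected.

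**Conclusion.** The point holds for the end-of-study STI comparison: as planned it is biased against iTAB if iTAB improves study retention. At equal true rates of 0.2 to 0.9 per person-year, with all randomized as denominator, week-48 dropout of 30% vs 15% gives a risk ratio of 1.11 to 1.14 and 8 to 23% false positives. With 20% vs 15% it is about 1.04 and 4 to 6%, which is close to nominal. With equal dropout there is no bias. At week 48 the false-positive rate is 5 to 11% at 30% vs 15%. For HIV only the estimate is affected.

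The direction is firm given better retention with iTAB. The size is not, because it rests on assumed infection rates, an assumed dropout gap and a denominator that the plan leaves open. It is worth correcting because the remedy is cheap, but it does not touch the primary analysis.

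**What to change.** In Protocol 9.6.4 and SAP 7.2 and 7.3:
- Make the end-of-study STI comparison events per person-year with a rate ratio (Poisson or negative binomial, with arm and site, and log time at risk to last test as offset). Alternatively use time to first new STI with dropouts censored at last test. Allow for 24-weekly detection by interval-censored or discrete-time methods; a plain log-rank test ignores it.
- Report HIV as events per person-year by arm, with a rate ratio.
- Keep all mITT participants. Those never tested after baseline contribute no time at risk and are counted by arm. Restricting the population to tested participants would condition on retention, the quantity that may differ.
- Keep the Fisher proportions at both horizons as descriptive, with the denominator stated, and call them proportions.
- Reconcile the 96-week limit (Protocol 5.1.3) with about 2.5 years (SAP section 2). The latter may mean the length of the study rather than of one person's follow-up, but the end-of-study horizon depends on it.

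The cost is SAP wording and one model on visit and test dates already collected. The downside is a model assumption for a secondary outcome. Informative dropout is not removed, so retention by arm should be shown beside the result.

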10.0 PHARMACOLOGY PLAN

10.1 Sample Assay Methods

FTC concentrations will be measured in the Pediatric Clinical Pharmacology Laboratory of the University of California, San Diego by a validated, Liquid Chromatography-Mass Spectrometry (LC-MS) method. The laboratory is registered with the ACTG Quality Assurance/Quality Control proficiency testing program [27] and successfully completes proficiency testing for the accuracy and precision of the FTC assay every 6 months. Inter-assay variability is less than 6% for low, middle and high controls. The lower limit of detection of FTC is approximately 1 ng/mL (the lower limit of quantitation is 11.8 ng/mL). For qualitative assays, unknown samples will be measured in the presence of internal standard to determine if the FTC ion peak is present (≥ 1 ng/mL) or absent (< 1 ng/mL). Stored plasma samples will be bulk testing of qualitative presence of FTC at the end of follow-up. Additional pharmacology analyses will be done in retrospect and the specific analysis will be included in the SAP prior to data log and sample testing.

11.0 DATA COLLECTION AND MONITORING AND ADVERSE EVENT REPORTING

11.1 Records to be Kept

Case report forms (CRFs) will be provided for each subject. Subjects must not be identified by name on any CRFs. Subjects will be identified by the PID provided by the CCTG Data Unit upon registration and the linkage to the PID will be kept in paper copy only in a locked cabinet in a secure office at the study sites available only to the site investigators.

Subject self-reported surveys that are performed electronically will be automatically stored in the electronic database secured by the CFAR BIT group for the CCTG.

11.2 Role of Data Management

11.2.1 Instructions concerning the recording of study data on CRFs will be provided by the CCTG Data Unit.

11.2.2 It is the responsibility of the CCTG Data Unit to assure the quality of computerized data for this study.

11.3 Clinical Site Monitoring and Record Availability

11.3.1 Site monitors provided by the CCTG will visit participating clinical research sites to review the individual subject records including consent forms, CRFs, supporting data, laboratory specimen records, and medical records (e.g., physician progress notes, nursing notes, individual hospital charts), to ensure protection of study subjects, compliance with the protocol and accuracy and completeness of records. The monitors also will inspect sites's regulatory files to ensure that regulatory requirements are being followed.

11.3.2 The investigator will make study documents (e.g., consent forms and CRFs) and pertinent hospital or clinic records readily available for inspection by the local IRB or the site monitors.

11.4 Serious Adverse Experience (SAE) Reporting

Serious adverse events are not expected in this study. All SAEs must be documented on the SAE Reporting Form within 5 working days of site awareness of the event and submitted to the CCTG Data Unit.

12.0 HUMAN SUBJECTS

12.1 Institutional Review Board (IRB) Review and Informed Consent

This protocol and the informed consent document and any subsequent modifications will be reviewed and approved by the IRB or ethics committee responsible for the oversight of the study. A signed consent form will be obtained from the subject. The consent form will describe the purpose of the study, the procedures to be followed and the risks and benefits of participation. A copy of the consent form will be given to the subject.

12.2 Subject Confidentiality

All laboratory specimens, evaluation forms, reports, and other records that leave the site will be stripped of any patient identifiers (name, birthdate, medical record number) and only identified by the coded PID in order to maintain subject confidentiality. All records will be kept locked. All computer entry and networking programs will be done with coded numbers only and analyzed centrally without any possibility of linking subject identity with subject data. Clinical information will not be released without written permission of the subject, except as necessary for monitoring by IRB and governmental agencies.

12.3 Study Discontinuation

The study may be discontinued at any time by the IRB or other government agencies as part of their duties to ensure that research subjects are protected.

13.0 PUBLICATION OF RESEARCH FINDINGS

Publication of the results of this trial will be governed by CCTG policies. Any presentation, abstract or manuscript will be made available for review by pharmaceutical supporters prior to submission.

